The research plan

Clinical study protocol for safety and precision of radial artery catheterization

Research unit: Nanjing First Hospital

Department undertaken by: Department of
Anesthesiology

Contact number: [name]

Participating units: Nanjing Jiangning Hospital of
Traditional Chinese Medicine

Years of study: July 2023–June 2024

Version number: V1.0

Version date: 22nd July, 2023

scenario summary

research design (Can be selected more)	 case-control study  cohort study  cross-sectional study  Randomized controlled study  applied the blind method  other:
Study type (Please follow the project)	 Concomitant diagnostic kit study  Retrospective study of previous clinical data
Type check	 Retrospective study of previous clinical specimens  Establish a specimen library study  Establish a cohort study  Previous individual cases were reported  Study of non-implantable medical devices (face mask, dental pad, etc.)  Five years of marketed drug study (including chemical drugs, generic drugs, etc.)  Listed device study (including AI, imaging software)  Others (for the investigator's judgment, please specify:)
Total number of cases	100 Cases
Risk / benefit analysis	
Risk: The study may have a radial artery puncture injury;
 
Benefits: Select a more appropriate and safe and accurate location for clinical practice as an ultrasound-guided radial artery puncture placement
 
Pipe parts.

risk judgement	 Not greater than the minimum risk  is greater than the minimum risk
	Minimum risk: the likelihood and extent of expected risk in the trial is not greater than routine or routine

	Risk of grid examination or psychological testing
The study period	From 22 July 2023 to 30 June 2024

1. research background

With the continuous development and clinical popularization of invasive blood pressure monitoring technology (ABP), the safety of patient anesthesia has been greatly guaranteed. The radial artery is superficial, and the forearm has a dual blood supply to the radial and ulnar arteries, thus becoming an arterial puncture

The first choice for catheterization.

It has been reported that the distal quarter of the forearm is the best insertion site for ultrasound-guided radial artery puncture, and the selection of the radial forearm catheterization improves the success rate and the overall success rate of the first puncture attempt

Prevalence of hematoma during the puncture process.

Invasive radial artery puncture sometimes cannot completely avoid complications, such as puncture hematoma and artery closure. Complications such as plug, infection, pseudoaneurysm, vasospasm, and neurovascular injury have been reported in the literature.

There are no recommendations for the best puncture site for radial artery puncture. Therefore, the choice is more appropriate and safe. Fully accurate location as ultrasound-guided radial artery puncture and catheterization is particularly important.

2. purpose of research

1. Main objective: To evaluate the anatomical parameters of the radial artery based on ultrasound imaging in the forearm,

Provide a reference to ultrasound anatomy for the clinical implementation of radial artery puncture.

2. Secondary objective: To find the best site of radial artery puncture to improve the safety and accuracy of radial artery puncture and catheterization.

3. Study design, methods, and study procedures

1. Study design

In this study, we plan to further compare the position distance between the radial artery and the ulnar artery, the vertical distance from the radial artery (center), and the distance between the radial artery (ulnar: radial)

The influence of age, BMI and left and right side on the radial artery position.

At the same time, the radial movement is intended to be guided by ultrasound at different distances during the radial artery puncture

Success rate of first puncture, puncture catheterization time, number of puncture and puncture related complications.

The sample size of this study was calculated according to the results of the pretest. The main observation indicators were the vertical distance between the radial artery and the radial artery (radial artery), set statistical efficiency $1 - \beta = 0.9$, test standard $\alpha = 0.05$, $n = 30$, calculated $n = 30$, the case loss rate was set at 15%, and the final sample size was 100 example.

2. Research methods

The anatomical relationship and influencing factors of the radial artery were observed by ultrasound, and then the optimal puncture position was selected and the puncture was guided Reduce the number of punctures, reduce the complications, and improve the safety and precision.

3. Study steps

Main study steps: patients in the supine position, both upper limb abduction, palm up, wrist angle of 45°, using a portable ultrasound instrument (probe frequency 13–6 MHz, Sonosa), the ultrasound probe in the direction of the short axis in the radial artery (from the radial artery) to the radius for the projection of the radial artery, the relative distance of each anatomical site was 2cm. There was no significant compression of the radial artery to maintain the normal shape and site of the vessel. The radial diameter of the radial artery, the vertical distance from the skin, and the radial god were measured Distance relative to the radial artery (ulnar: radial). And recorded according to gender, age, BMI, and left and right sides.

Secondary study objective steps: the radial artery surface projection was divided into three sections. The first segment is in the

range of 0–5cm from the proximal to the radial stem, the second segment is in the range of 5–10cm from the proximal to the radial stem, and the third segment is in the range of 10cm to the proximal cubital fossa. And the puncture site was divided into the first stage of the left hand, the second section of the left hand, the third section of the left hand, the first section of the right hand, the second stage of the right hand, and the third section of the right hand; the experimenter randomly selected the puncture site, and used the portable ultrasound instrument (probe frequency 13–6 MHz, Sonos), and the in-plane puncture technique was used to puncture the radial artery, and the first puncture success rate, puncture insertion time and puncture times were recorded

And puncture-related complications.

4. Case selection

1. Inclusion criteria: (1) patients undergoing elective surgery scheduled to undergo general anesthesia and invasive arterial blood pressure monitoring; (2) ASA grade I~; (3) age 18 to 65 years; (4) agree to participate in this clinical study and sign the informed consent form.

2. Exclusion criteria: (1) Allen positive or suspicious positive patients; (2) peripheral vascular diseases; (3) coronary artery related diseases; (4) local skin infection, rupture, scar and surgical history; (5) shock patients or acceptance, heart drugs, vasoreduction drugs; (6) peripheral nerve injury, anatomical abnormalities and neurological abnormalities; (7) upper limbs

The atic, not unable to complete the ultrasound assessment.

3. Termination criteria: Patients may withdraw their consent and withdraw from the trial at any time.

Any medical condition in the study that poses a risk that the continuing study subject may be terminated by the study physician

Continued to participate in this study;

And the study physician may terminate if the patient fails to comply with the study plan, or if a study-related injury occurs

Continue to participate in this study;

The investigator judged the other conditions that should be withdrawn from the trial.

5. Other alternative methods of diagnosis and treatment are available

If the radial artery puncture is unsuccessful, non-invasive blood pressure monitoring of the upper arm cuff is feasible.

Vi. Test items and test time points

After entering the patient into the room, the position distance between the radial artery (the radial artery, radial artery, radial artery, radial artery (center) vertical distance from the skin, and the distance of the radial nerve (ulnar: radial side) were measured. At the same time, the first puncture of radial artery puncture at different distances of the forearm was recorded

Power, puncture and catheterization time, number of puncture times, and puncture-related complications.

7. Efficacy evaluation criteria

Complete and accurately record all data, operation time, frequency and success rate.

Viii. Observation, recording and disposal of adverse events

You will be followed up and evaluated within 3 days of the study. In case of serious radial artery puncture complications during the experiment, the experiment will be stopped immediately, and the adverse events will be recorded and reported to the project leader. Positive and effective

Follow-up records according to the type of complications.

IX. Research quality control and quality assurance

not have

X. Data security monitoring

The clinical study will develop a corresponding data safety monitoring plan according to the risk size. All bad events should be recorded in detail, properly handled and tracked until properly resolved or in stable condition, and timely submitted to the ethics committee and the competent department in accordance with the regulations. Door, sponsor and drug to report serious adverse events and unexpected events; principal investigator regularly

A cumulative review of all adverse events and an investigator meeting if necessary to assess the risks and benefits of the study; both Emergency unblinding may be performed when necessary to ensure subject safety and equity.

Xi. Statistical treatment

Using SPSS 22.0 software, the measurement data with mean \pm standard deviation ($\bar{x} \pm s$), ANOVA between groups; count data are presented as example or percentage, with t test, $P < 0.05$. The difference was statistically significant.

Xii. Ethics principles and requirements for clinical research

Clinical studies will follow the Declaration of Helsinki of the World Medical Congress and the Measures of the National Health and Family Planning Commission of the People's Republic of China, and implement informed consent,

Protect privacy, research free and compensation, risk control, special subject protection and compensation principles and requirements for research related damages. The clinical study was performed before EC approval of the study protocol. Before each subject is enrolled in the study, the Investigator has the responsibility to fully and comprehensively present the purpose, procedures and possible risks of the study, and their legal representative and to sign a written informed consent form that their participation in the clinical study is entirely voluntary, that they may refuse to participate or withdraw from the study at any stage of the trial without discrimination and retaliation, and their medical treatment and interests are not affected. The informed consent form should be kept as a clinical study document for future reference to effectively protect the personal privacy and data confidentiality.

Xiii. Research progress

July 2023–August 2023: Trial implementation

August 2023–March 2024: Collect and collate data

March 2024– June 2024: Writing the paper

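### Complications by puncture site are to be summarised only by percentages and P < 0.05; at about 28 patients per segment, exact intervals and a limit on the safety claim are needed

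*SAP*

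**What the plan says.** Section 2 of the SAP (purpose of research) sets the secondary objective: "To find the best site of radial artery puncture to improve the safety and accuracy of radial artery puncture and catheterization". The study design paragraph in section 3 lists the outcomes to be compared across puncture distances: "Success rate of first puncture, puncture catheterization time, number of puncture and puncture related complications". The background names types of complication ("Invasive radial artery puncture sometimes cannot completely avoid complications, such as puncture hematoma and artery closure", with more in the sentence that follows) but gives no rate for any of them.

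The study steps divide the artery into three segments and, by hand, into six puncture sites, with the site chosen at random. No allocation ratio is given.

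The only analysis rule for complications is the general line in Xi. Statistical treatment: "count data are presented as example or percentage, with t test", with P < 0.05 called significant. Xi mentions no confidence interval, no margin and no rule for reading a non-significant result. The sample size rests on an anatomical measurement ("The main observation indicators were the vertical distance between the radial artery and the radial artery (radial artery"), not on complications.

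**The concern.** The study is meant to name a better and safer puncture site, and complications by site are the outcome that bears on safety most directly. A bare percentage from a group of this size says little, and a P value above 0.05 does not say how large a difference remains possible. A results line of 0% against 4% with P > 0.05 could be taken to mean that the segments are equally safe, or that the segment without events is safe. The same data would be compatible with a substantial complication risk in either segment and a substantial difference between them.

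Replacing the t test with a test suited to proportions would not cure this, because at low event counts a suitable test is also uninformative when it is non-significant. The gap is the missing interval and the missing limit on what may be concluded.

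**Working it through.** **Inputs from the SAP.** Final sample size 100; loss 15%; three segments; six sites (three segments by two hands); threshold P < 0.05.

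**Assumptions.** Equal allocation, one puncture per patient, the full 15% loss, two-sided tests, and the t test applied to 0/1 outcomes of two segments. All complication rates below are assumed, since the SAP gives none.

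**The plan's own figure.** The SAP reports "calculated $n = 30" and reaches 100 after 15% loss, without saying whether 30 is a total or per group. Inflating by N/(1 − 0.15) gives 30 → 36, 60 → 71, 90 → 106 and 180 → 212, so 100 is not reproduced on any of these readings. That is a separate matter; 100 is taken as stated here.

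**Group size.** 100 × 0.85 = 85. Then 85/3 = 28.3, about 28 per segment with hands pooled, and 85/6 = 14.2, about 14 per site. With no losses, 100/3 = 33.3, about 33 per segment.

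**What an observed count leaves open.** For zero events the Clopper-Pearson two-sided 95% upper limit is 1 − 0.025^(1/n):
- n = 28: 1 − 0.025^(1/28) = 12.3%
- n = 33: 1 − 0.025^(1/33) = 10.6%
- n = 14: 1 − 0.025^(1/14) = 23.2%

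For x > 0 events the limits are the beta quantiles B(0.025; x, n − x + 1) and B(0.975; x + 1, n − x):
- 1/28: 0.1% to 18.3%
- 2/28: 0.9% to 23.5%

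So a segment with no events in 28 patients would still be compatible with a risk of about 1 in 8.

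**What a comparison leaves open.** For 0/28 against 1/28, the Newcombe (score-based) 95% interval for the difference runs from about −9% to +18%. If one segment has 0/28, another needs at least 6/28 (21%) for Fisher P < 0.05, and 4/28 (14%) for the planned t test. At 0/28 against 5/28, Fisher gives P = 0.051 while the Newcombe interval is about 2% to 36%. The P value alone conveys none of that width.

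**Power at 28 per segment.** For rates p1 and p2, power is the sum of Bin(a; 28, p1) × Bin(b; 28, p2) over all pairs (a, b) with P < 0.05, by exact enumeration. The three-segment column uses an exact test across segments, with two segments at p1 and one at p2.

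| Assumed rates | Fisher, two segments | t test, two segments | Exact test, three segments |
|---|---|---|---|
| 2% v 10% | 3% | 19% | 16% |
| 5% v 10% | 2% | 10% | 6% |
| 5% v 15% | 8% | 24% | 20% |
| 5% v 20% | 21% | 43% | 39% |
| 5% v 30% | 58% | 75% | 76% |
| 5% v 40% | 86% | 93% | 95% |

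With 33 per segment, Fisher's power is 6% (2% v 10%), 12% (5% v 15%) and 29% (5% v 20%).

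**The case against.** The strongest reply is that the SAP never calls complications rare and gives no rate. If haematoma is counted and differs widely between segments, power is reasonable: 58% to 95% across the three tests for 5% against 30% or 40%. A reader might infer that a non-significant result is almost certain whatever the truth; the table shows that this fails at higher rates. Pairwise Fisher is also the least favourable of the three tests, and it is not the planned one. This stands, and it is why the full range is shown.

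A reader might also infer that the plan intends to read P > 0.05 as equal safety. It does not say so. The stated aim is to find a better site, and no equivalence or non-inferiority conclusion appears anywhere. The misreading is a risk that Xi leaves open, not something it states.

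Third, safety is not watched only through this test. Section Viii provides a 3-day follow-up, section X provides a cumulative review of adverse events, and the number of punctures is recorded and linked to safety. These provisions protect patients and add context, but they do not supply a comparison of complication risk between sites.

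Finally, a rule that a segment may be called safer only if the interval for the difference excludes zero would in effect be a 5% test again, over three unadjusted pairs. That is correct, and such a rule is not part of the fix.

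None of these replies removes the need for intervals.

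**Conclusion.** The point holds as a weakness in the stated analysis rule and should be corrected. Percentages with P < 0.05 do not show how little about 28 patients per segment can say about complications: an upper limit of 12.3% after zero events, 0.1% to 18.3% after one, and 23.2% after zero events at a single site of about 14.

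A non-significant result is likely if complications are uncommon. With about 5% or less in most segments and 10% in the worst, power is at most 19% by any of the three tests. It is not certain, and it becomes unlikely if the worst segment reaches 40% against 5%. The group sizes rest on an equal split, one puncture per patient, the full 15% loss and, for 28, pooled hands; the event rates are assumed throughout. The interval limits do not depend on the assumed rates.

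**What to change.** In Xi. Statistical treatment, give complications their own rule:
- Report events/N per segment with Clopper-Pearson 95% confidence intervals, and between-segment risk differences with exact or score 95% confidence intervals, as the main summary.
- If a test is kept, use one overall exact test across segments (Fisher-Freeman-Halton) in place of the t test, and adjust any pairwise claim for multiplicity.
- State that P > 0.05 or zero events will not be taken as evidence that the segments are equally safe or that a segment is safe.

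The cost is wording in the SAP and a few extra columns in one table. No further patients or data are needed. The downside is a more modest safety conclusion.

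### The plan asks how age and BMI influence radial artery position but names only a between-groups ANOVA, with no cut points, no regression and no joint model

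*SAP*

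**What the plan says.** The SAP's section 3, under Study design, lists among its questions "The influence of age, BMI and left and right side on the radial artery position". Under Study steps, the measurements are to be taken at sites 2 cm apart along the artery, "And recorded according to gender, age, BMI, and left and right sides". Sex is therefore recorded, although the Study design list leaves it out. Section 4 admits patients of "age 18 to 65 years".

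Section Xi covers the whole statistical treatment in one sentence. Measurement data are summarised as mean and standard deviation, and the tests are "ANOVA between groups; count data are presented as example or percentage, with t test". Regression, correlation, covariate adjustment and multi-factor models are not mentioned. No age or BMI groups are defined anywhere, and the section does not say whether the ANOVA has one factor or several.

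**The concern.** Side is a two-level factor and fits an ANOVA. Age and BMI do not: a between-groups comparison can use them only after each has been divided into categories. Dividing them discards the variation within each category and so lowers power. Because the categories are not fixed in advance, they can also be chosen after the data are seen.

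A second question is whether the factors are analysed together. If age groups are compared without regard to BMI, and older patients in the sample tend to have a different BMI, a difference in artery depth that belongs to BMI will appear as a difference by age. The plan asks about the influence of each factor, so this bears directly on what it can conclude.

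**Working it through.** **Inputs from the SAP.** Two-sided alpha 0.05 (sidedness is not stated and is assumed). Design power 0.9. Sample size: "the case loss rate was set at 15%, and the final sample size was 100 example". Analysable patients: 100 × (1 − 0.15) = 85.

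**The plan's own figure.** The calculated n is 30, with no effect size or standard deviation, so it cannot be rebuilt. Dividing by 0.85 and rounding up, 30 gives 36, 60 gives 71, 90 gives 106 and 180 gives 212. None of these is 100. That is a separate matter, and nothing below depends on how 100 was reached.

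**Assumptions not in the SAP.** One depth value per patient, normally distributed variables, factor-depth correlation r from 0.2 to 0.5, BMI-depth correlation b from 0.4 to 0.6, and age-BMI correlation c from 0 to 0.4.

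**Step 1: power lost by grouping.** With the factor continuous, power is approximately Φ(√(n − 3) × atanh(r) − 1.96). For r = 0.3 and n = 85: √82 × 0.3095 = 2.80, and Φ(0.84) = 80%. A median split of a normal factor multiplies the correlation by √(2/π) = 0.798, so 0.3 becomes 0.239. Then √82 × 0.2441 = 2.21, and Φ(0.25) = 60%. Simulation with two, three and four equal-sized groups (20,000 data sets per setting) gives, at n = 85:

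| Assumed r | Continuous | ANOVA, 2-4 groups |
|---|---|---|
| 0.2 | 46% | 26-31% |
| 0.3 | 80% | 57-61% |
| 0.4 | 97% | 86-87% |
| 0.5 | over 99% | 98% |

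The loss is about 15-20 points at r = 0.2, 19-23 at 0.3, 10-11 at 0.4, and almost nil at 0.5. At r = 0.34, where the continuous test reaches the plan's 90%, grouped ANOVA reaches 71-73%.

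**Step 2: misattribution, if age is tested alone.** Suppose age has no effect of its own. Its marginal correlation with depth is then c × b. For c = 0.3 and b = 0.6 this is 0.18; after a median split it is 0.18 × 0.798 = 0.144. Then √82 × 0.1446 = 1.31, and Φ(1.31 − 1.96) = 26%. Simulated rejection rates for age, over two to four groups and b = 0.4-0.6, at n = 85:

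| Assumed age-BMI correlation | False-positive rate for age |
|---|---|
| 0 | about 5% |
| 0.1 | 6-7% |
| 0.2 | 8-14% |
| 0.3 | 12-26% |
| 0.4 | 18-43% |

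**Step 3: does a joint model help?** At n = 100 and b = 0.5, an additive two-way ANOVA on median splits of age and BMI rejects for age in about 8% of runs at c = 0.3 and 12% at c = 0.5, against 20-22% and 51-52% for a one-way ANOVA. Regression with both factors continuous stays at about 5%.

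**The case against.** A reader might infer that the factors must be tested one at a time, and that age will therefore be credited with the effect of BMI. The document supports neither step. ANOVA between groups does not exclude a multi-factor ANOVA, which would remove most of the misattribution, though not all of it, because both factors would still be cut. Misattribution also needs age and BMI to be correlated in this sample. The SAP gives no such figure, and at a correlation of zero there is none.

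The power loss has limits too. It depends on an effect size that the documents do not give, and it nearly vanishes when the factor is strongly related to depth. The familiar figure that grouping keeps 2/π = 64% of the information belongs to a median split of a normal factor, which the plan does not specify. A linear trend contrast across the groups would recover part of the loss: 70% power with three groups and 73% with four at r = 0.3 and n = 85, against 60% and 56% for the overall test. The plan names no such contrast.

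On weight, neither of the two numbered objectives mentions age or BMI, the sample size is not tied to them, and the line that does mention them is a fragment of translated text. This lowers the importance of the point. It does not remove the mismatch, since the influence of these factors is a stated question and the only method named for it suits categories.

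**Conclusion.** The point holds in this form. The plan poses a question about two continuous factors and names only a method that requires them to be grouped, without saying how. Under moderate assumed correlations (0.2-0.4) this costs roughly 10 to 23 points of power at n = 85; at 0.5 it costs very little. The risk of crediting age with an effect of BMI is conditional on separate testing and on correlated factors; it ranges from none to a false-positive rate of 43% over the values assumed here. The grouping and the open cut points follow from the text. All the sizes rest on assumed correlations. The change is worth making because it is cheap and answers the question as posed.

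**What to change.** In section Xi, replace ANOVA for the influencing factors with one regression model per measurement. The model should contain age and BMI as continuous terms, together with sex, side and distance along the artery. Include a patient random effect, because the Study steps have sites 2 cm apart, on left and right sides, measured in the same patient. Report the slopes for age and BMI with 95% confidence intervals. Add sex to the factor list under Study design so that it matches the Study steps. If age or BMI groups are wanted, keep them as a descriptive table only.

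The cost is wording: every variable is already recorded, and neither the design nor the conduct changes. The one added task is to check that linear terms for age and BMI are adequate.

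### The list of factors for radial artery position omits sex in the design but includes it in the study steps, and the statistics section names no joint model, so sex may be collected but not analysed

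*SAP*

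**What the plan says.** Four places in the SAP bear on this.

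- **Section 3, item 1 (Study design)** names three influences to be studied: "The influence of age, BMI and left and right side on the radial artery position".
- **Section 3, item 2 (Research methods)** refers to such influences without listing them: "The anatomical relationship and influencing factors of the radial artery were observed by ultrasound".
- **Section 3, item 3 (Study steps, main steps)** says of the anatomical measurements: "And recorded according to gender, age, BMI, and left and right sides". That is four factors.
- **Section Xi (Statistical treatment)** gives the method as "ANOVA between groups; count data are presented as example or percentage, with t test", with significance at P < 0.05. It does not say which factors are tested, whether they are tested together, or whether any covariate is adjusted for.

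The sample size paragraph gives 100 patients in total: "the case loss rate was set at 15%, and the final sample size was 100 example".

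**The concern.** The same measurements come with two factor lists that match except for sex, and the statistics section does not say which is analysed. An analyst who follows the design would leave out a patient factor that has been recorded. One who follows the study steps would include it. That choice should not be open once the data have been seen.

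Two things are at stake. First, the main objective is an ultrasound-anatomical reference for puncture. If sex is left out, that reference does not separate men from women, although the data to do so are in hand. Second, if sex is related both to the measurement and to BMI or age, an unadjusted association with BMI or age could in part be a sex difference.

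**Working it through.** **Step 1. The texts side by side**

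| Place in the SAP | Factors |
|---|---|
| Study design | age, BMI, side |
| Research methods | influencing factors, not listed |
| Study steps | gender, age, BMI, side |
| Section Xi | none named; ANOVA between groups, t test |

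The first and third rows differ by exactly one item. The last row does not resolve the difference. The document states no figure on this point, so there is none to reproduce.

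**Step 2. What could follow if sex is left out**

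The document gives neither a sex effect nor a sex-BMI relation. The following inputs are therefore assumptions, apart from the patient numbers and the 5% level (two-sided assumed):

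- n = 85 analysable patients, from 100 × (1 − 0.15), or all 100;
- equal numbers of men and women;
- no BMI effect once sex is held fixed;
- sex difference in the measurement of d within-sex SDs;
- one value per patient.

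With equal sexes, the correlation of sex with the measurement is d/√(d² + 4), and its square is the share of variance due to sex:

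- d = 0.5: 0.25/4.25 = 0.059
- d = 0.8: 0.64/4.64 = 0.138

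If sex and BMI have correlation r, the BMI test without sex has a noncentrality of about √n × r × d/√(d² + 4). For n = 85, d = 0.8 and r = 0.3 this is 9.22 × 0.3 × 0.371 = 1.03. The two-sided rejection rate is then P(Z > 1.96 − 1.03) + P(Z < −1.96 − 1.03), about 17.7%. For d = 0.5 and r = 0.3 the noncentrality is 9.22 × 0.3 × 0.243 = 0.67 and the rate is about 10.3%. With r = 0 the rate is 5%.

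**Step 3. Simulation with continuous BMI** (n = 85, linear regression, 4,000 runs per scenario)

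| d | r = 0.1 | r = 0.2 | r = 0.3 |
|---|---|---|---|
| 0.5, sex omitted | 5.5% | 7.8% | 10.0% |
| 0.8, sex omitted | 6.2% | 10.2% | 17.2% |

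With sex in the model, the rate is 4.5% to 5.3% throughout.

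**Step 4. Simulation with grouped BMI, closer to the stated ANOVA** (n = 100, BMI split at the median, 4,000 runs per scenario)

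One-way ANOVA on BMI group, without sex:

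| d | BMI difference between sexes: 0 SD | 0.2 SD | 0.4 SD | 0.6 SD |
|---|---|---|---|---|
| 0.3 | 4.8% | 5.9% | 5.3% | 6.6% |
| 0.5 | 5.3% | 5.3% | 7.4% | 8.5% |
| 0.8 | 5.0% | 6.6% | 8.5% | 13.7% |

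With sex in the same model, the rate is 4.7% to 5.5% throughout. A BMI difference of 0.6 SD corresponds to r = 0.6/√(0.36 + 4) = 0.29, so the last column is close to r = 0.3 in Step 3.

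**Step 5. What removes the excess**

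Adding sex to the list with its own one-way ANOVA leaves the BMI test, and therefore its error rate, exactly as it was. Only fitting sex and BMI together brings the rate back to about 5%.

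**The case against.** **The two lists may do different jobs.** The design names influences of interest; the study steps describe recording. Recording a variable without studying it as an influence is ordinary practice, and recording by gender can even be read as a planned breakdown by sex. This stands in part: the lists need not be a flat contradiction. But neither reading is confirmed in section Xi, so the analysis remains open.

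**The mismatch does not itself create a false effect.** A reader might infer that, because sex is missing from the design list, a sex difference will be reported as a BMI or age effect. The document does not support that. Section Xi plans no adjusted analysis, so BMI would be just as unadjusted if sex stood in both lists, and age and BMI could confound each other in the same way. This stands in full. The risk comes from the unspecified model, and it needs a relation between sex and BMI or age that the document does not give.

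**An unadjusted association is legitimate in a descriptive reference.** The main objective names no patient factors; they enter only in the design paragraph. Calling a BMI association a false positive presumes that the sex-adjusted effect is the target, which the plan never says. This also stands, so the rates above apply only to that target.

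**The text may be damaged.** The design sentence is a fragment after a broken line, and nearby wording is garbled, so a lost word cannot be excluded. The list itself reads as complete, however, and the fix is the same either way.

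**Conclusion.** The point holds in a limited form. The factor lists disagree on sex, and section Xi specifies neither the factors nor a joint model. If the design list is followed with separate ANOVAs, a recorded patient factor goes unanalysed and the anatomical reference is not split by sex.

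Confounding of a BMI or age association by sex is possible but not demonstrated. For a sex-adjusted BMI effect, the false-positive rate ranges from about 5% when sex and BMI are unrelated to about 14% (BMI grouped, n = 100) or 17% (BMI continuous, n = 85) at the upper end of the assumed ranges, against about 5% with sex in the model. Those figures rest on assumed sex differences and on one value per patient, whereas the plan measures both arms at several sites. No figure was computed for age, so the possibility there is qualitative only.

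This is worth correcting because the data are already being collected, not because a bias has been shown.

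**What to change.** 1. Use one factor list, namely sex, age, BMI and side, in both the study design and the study steps.
2. In section Xi, replace separate ANOVAs for these factors with one joint model for each anatomical measurement. It should contain all four factors and a random effect for patient, because both arms and several sites are measured in each patient.
3. Report the anatomical reference values by sex.

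The first step without the second leaves the BMI and age tests unadjusted.

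The cost is a few sentences of text, one model in place of separate ANOVAs, and one degree of freedom for sex. Sex is already recorded, so no new data or patients are needed. If sex proves unrelated to the measurement, or to age and BMI, the age and BMI results should change little.
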